7.7.2. Growth Factor Therapy

Growth factors should not be administered to a patient to satisfy study inclusion criteria.

Growth factors may be administered in accordance with ASCO guidelines (Smith et al. 2015). Dosing of abemaciclib must be suspended if the administration of growth factors is required and must not be recommenced within 48 hours of the last dose of growth factors having been administered. Following the administration of growth factors, the dose of abemaciclib must be reduced by 1 dose level on recommencement, if a dose reduction for the specific event necessitating the use of the growth factors has not already occurred.

7.8. Treatment after the End of the Study

Study completion will occur following the final analysis of overall survival, as determined by Lilly. Investigators will continue to follow the Schedule of Activities (refer to Section [2](#)) for all patients until notified by Lilly that study completion has occurred.

7.8.1. Continued Access

Patients who are still on study treatment at the time of study completion may continue to receive study treatment if they are experiencing clinical benefit and no undue risks ([Figure JPCG.2](#)).

Continued access period will apply to this study only if at least 1 patient is still on abemaciclib when study completion occurs. Lilly will notify investigators when the continued access period begins.

Patients who are in short-term follow-up when the continued access period begins will continue in short-term follow-up until the 30-day short-term follow-up visit is completed. Long-term follow-up does not apply.

Patients who are in long-term follow-up when the continued access period begins will be discontinued from long-term follow-up.

During the continued access period, all AEs, SAEs, and abemaciclib exposure will be reported on the eCRF at least every 28 days when drug is returned and dispensed. SAEs should be reported immediately and patients should not wait for a drug return/dispensing visit. SAEs will also be reported to Lilly Global Patient Safety. In the event that an SAE occurs, Lilly may request additional information (such as local laboratory results, concomitant medications and hospitalizations) in order to evaluate the reported SAE.

Investigators will perform any other standard procedures and tests needed to treat and evaluate patients; however, the choice and timing of tests will be at the investigator’s discretion. Lilly will not routinely collect the results of these assessments.

Follow-up procedures will be performed as shown in the Continued Access Schedule of Activities (Table JPCG.4).

[figure not shown]

Figure JPCG.2. Continued access diagram.

8. Discontinuation Criteria

8.1. Discontinuation from Study Treatment

Patients will be discontinued from study treatment in the following circumstances:

- the patient is enrolled in any other clinical trial involving an investigational product or any other type of medical research judged not to be scientifically or medically compatible with this study
- investigator decision
 - the investigator decides that the patient should be discontinued from the study or study drug
 - if the patient, for any reason, requires treatment with another therapeutic agent that has been demonstrated to be effective for treatment of the study indication, discontinuation from the study drug occurs prior to introduction of the new agent
- patient decision
 - the patient requests to be withdrawn from the study or study drug
 - the patient's designee (for example, parents, legal guardian, or caregiver) requests that the patient be discontinued from study treatment
- sponsor decision
 - Lilly stops the study or stops the patient's participation in the study for medical, safety, regulatory, or other reasons consistent with applicable laws, regulations, and good clinical practice (GCP)
- the patient becomes pregnant during the study. See Section 9.2 regarding regulatory reporting requirements on fetal outcome and breastfeeding.
- the patient is significantly noncompliant with study procedures and/or treatment
- disease progression
- unacceptable toxicity

Patients who are discontinued from study treatment will have follow-up procedures performed as shown in the Schedule of Activities (Table JPCG.3).

For patients who discontinue study treatment without objectively measured progressive disease, continue to evaluate tumor response according to planned tumor assessment schedule by the same method used at baseline and throughout the follow-up periods until patient has objective disease progression or until the study's primary analysis of PFS. After the patient has objective disease progression, radiologic tests are no longer required.

8.1.1. Discontinuation of Inadvertently Enrolled Patients

If Lilly or the investigator identifies a patient who did not meet enrollment criteria and was inadvertently enrolled, a discussion must occur between the Lilly CRP and the investigator to determine if the patient may continue in the study. If both agree it is medically appropriate to continue, the investigator must obtain documented approval from the Lilly CRP to allow the inadvertently enrolled patient to continue in the study with or without study treatment.

8.2. Discontinuation from the Study

Patients will be discontinued from the study in the following circumstances:

- participation in the study needs to be stopped for medical, safety, regulatory, or other reasons consistent with applicable laws, regulations, and GCP
- the patient becomes pregnant during the study. See Section 9.2 regarding regulatory reporting requirements on fetal outcome and breastfeeding.
- the investigator decides that the patient should be discontinued from the study
- the patient requests to be discontinued from the study
- the patient's designee (for example, parents, legal guardian, or caregiver) requests that the patient be discontinued from the study.

Patients who discontinue from the study early will have end-of-study procedures performed as shown in the Schedule of Activities (Table JPCG.3).

8.3. Lost to Follow-Up

A patient will be considered lost to follow-up if she repeatedly fails to return for scheduled visits and is unable to be contacted by the study site. Study site personnel are expected to make diligent attempts to contact patients who fail to return for a scheduled visit or who the site is otherwise unable to follow-up.

Study site personnel, or an independent third party, will attempt to collect the survival status for all randomized patients who are lost to follow-up, including randomized patients who do not receive study treatment, within legal and ethical boundaries. Public sources may be searched for survival status information. If the patient's survival status is determined, the survival status will be documented, and the patient will not be considered lost to follow-up.

Lilly personnel will not be involved in any attempts to collect survival status information.

9. Study Assessments and Procedures

Section 2 (Table JPCG.1, Table JPCG.2, and Table JPCG.3) provides the Schedule of Activities for this study.

Appendix 3 provides a list of the laboratory tests that will be performed for this study.

Appendix 4 provides the schedule for collection of samples in this study.

Unless otherwise stated in the following subsections, all samples collected for specified laboratory tests will be destroyed within 60 days after receipt of confirmed test results. Certain samples may be retained for a longer period, if necessary, to comply with applicable laws, regulations, or laboratory certification standards.

9.1. Efficacy Assessments

9.1.1. Efficacy Assessments at Baseline and during Study Treatment

Tumor assessments will be performed at baseline (within 28 days from first dose of study therapy) and every 8 weeks (- 7 days) by investigator. The same method of assessment and technique used at baseline should be used for each subsequent assessment thereafter.

Radiological scan of the chest, abdomen, and pelvis is required. See Section 10.3.1 for definitions of the efficacy endpoints. All tumor assessment images must be submitted for potential central review.

Computed tomography (CT) scans, including spiral CT, are the preferred methods of measurement (CT scan thickness recommended to be ≤ 5 mm); however, magnetic resonance imaging (MRI) is also acceptable in certain situations, such as when body scans are indicated or if there is a concern about radiation exposure associated with CT. Intravenous and oral contrast is required unless medically contraindicated.

The CT portion of a positron emission tomography (PET)-CT scan may be used as a method of response assessment if the site can document that the CT is of identical diagnostic quality to a diagnostic CT (with intravenous and oral contrast). A PET scan alone or as part of a PET-CT may be performed for additional analyses but cannot be used to assess response according to RECIST v.1.1 (Eisenhauer et al. 2009).

For only those patients with bone lesions identified by bone scintigraphy at baseline, directed imaging using one of the following methods will be performed at baseline: X-ray, CT scan with bone windows, or MRI. Directed imaging using the same method as at the baseline bone lesion assessment should be repeated every 8 weeks (-7 business days), and within 14 days of clinical progression.

For patients with visible tumors (such as skin lesions), photography will be performed at baseline and every 8 weeks (-7 business days), and within 14 days of clinical progression. Each photographic image of the tumor should include a ruler. Photographic images may be taken

more frequently based upon the discretion of the investigator or following the identification of new skin lesions postbaseline.

For patients continuing treatment during the Continued Access Period (after study completion), efficacy assessments (frequency and type of assessments) will be at the discretion of the investigator.

9.1.2. Efficacy Assessments during Postdiscontinuation Follow-up

Tumor assessments will be performed within 14 days of clinical progression and during postdiscontinuation follow-up as described in the Schedule of Activities (see Section 2).

For those patients who discontinue study treatment without objectively measured PD, the investigative sites will continue to monitor patients and periodically evaluate tumor response via radiological imaging and measurement of visible tumors (if applicable) approximately every 8 weeks from the first dose of study therapy by the same method used at baseline and throughout the study until the patient has objective disease progression or until primary analysis of PFS. In addition, anticancer therapies initiated after study treatment discontinuation will be collected during this follow-up period. After the patient has objective disease progression, radiologic tests and tumor assessments are no longer required and the patient will continue with postdiscontinuation follow-up approximately every 90 days until the patient's death or overall study completion. For patients with nonmeasurable bone lesions identified at baseline, bone scans are to be performed approximately every 24 weeks until objective disease progression or primary PFS analysis.

Lilly will continue to collect survival data on all patients but may reduce data collection for other efficacy data. Lilly will notify investigators when this reduced data collection can begin (see Section 7.8.1).

9.1.3. Appropriateness of Assessments

The measures used to assess safety and efficacy in this study are consistent with those used in most conventional oncology trials.

9.2. Adverse Events

The investigator will use Common Terminology Criteria for Adverse Events (CTCAE) Version 4.0 (NCI 2009) to assign AE terms and severity grades.

Investigators are responsible for:

- monitoring the safety of patients in this study and for alerting Lilly or its designee to any event that seems unusual, even if this event may be considered an unanticipated benefit to the patient
- the appropriate medical care of patients during the study
- documenting their review of each laboratory safety report
- following, through an appropriate health care option, AEs that are serious or otherwise medically important, considered related to study treatment or the study, or that caused

the patient to discontinue study treatment before completing the study. The patient should be followed until the event resolves, stabilizes with appropriate diagnostic evaluation, or is reasonably explained. Frequency of follow-up evaluation is left to the discretion of the investigator.

Lack of drug effect is not an AE in clinical studies, because the purpose of the clinical study is to establish treatment effect.

After the informed consent form (ICF) is signed, study site personnel will record via eCRF the occurrence and nature of each patient's preexisting conditions, including clinically significant signs and symptoms of the disease under treatment in the study. In addition, study site personnel will record via eCRF any change in the preexisting conditions and any new conditions as AEs. Investigators should record their assessment of the potential relatedness of each AE to study procedure or study treatment via eCRF.

The investigator will interpret and document whether or not an AE has a reasonable possibility of being related to study treatment or a study procedure, taking into account the disease, concomitant treatments, or pathologies. A "reasonable possibility" means that there is a cause and effect relationship between the study treatment and/or study procedure and the AE.

Planned surgeries and nonsurgical interventions should not be reported as AEs unless the underlying medical condition has worsened during the course of the study.

Study site personnel must report any dose modifications or treatment discontinuations that result from AEs to Lilly or its designee via eCRF, clarifying, if possible, the circumstances leading to the dose modification or discontinuation of treatment.

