7.4.1.1.2. Dose Delays and Omission

7.4.1.1.2.1. Abemaciclib

[Table JPCG.9](#) provides general guidelines for dose delays of abemaciclib.

Table JPCG.9. General Dose Delays of Abemaciclib

General Dose Delays	Time Permitted for Delay
Delay of a cycle due to holidays, weekends, bad weather, or other unforeseen circumstances	7 days
Toxicity-time for recovery to baseline or at least Grade 1 for nonhematologic and at least Grade 2 for hematologic toxicity	Up to 14 days

Both dose suspension (within a cycle) and cycle delay are permitted. When a dose suspension or cycle delay occurs related to toxicity (defined as an AE possibly related to study treatment per investigator judgment), abemaciclib and/or tamoxifen (Arm A only) may be suspended or delayed as determined by the investigator's judgment, but only for a maximum of 14 days.

Study treatment may be held up to 14 days within a cycle or at start of next cycle to permit sufficient time for recovery from the toxicity. If a dose suspension occurs within a cycle, the investigator may resume study drug dosing at the same dose level for the remainder of the cycle or, for abemaciclib only, at a reduced dose (assuming resolution to at least Grade 1 for nonhematological and at least Grade 2 for hematological toxicity). If the patient experiences the same toxicity with the same or greater severity (Common Terminology Criteria for Adverse Events [CTCAE] grade) requiring a dose suspension within a cycle or at start of the next cycle, the patient must be dose reduced for abemaciclib and not re-challenged a second time at the prior dose level (see [Table JPCG.7](#)).

Patients not recovering from toxicity within 14 days should be considered for discontinuation of study treatment. In exceptional circumstances, a delay >14 days is permitted upon agreement between the investigator and the Lilly CRP and abemaciclib dose adjustment is to be considered.

A delay of a cycle due to holiday, weekend, bad weather, or other unforeseen circumstances will be permitted for a maximum of 7 days and not counted as a protocol deviation. In exceptional cases of planned delays (including but not limited to vacation or holidays), additional study treatment may be dispensed.

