9.2.1. Serious Adverse Events

An SAE is any AE from this study that results in one of the following outcomes:

- death
- initial or prolonged inpatient hospitalization
- a life-threatening experience (that is, immediate risk of dying)
- persistent or significant disability/incapacity
- congenital anomaly/birth defect
- considered significant by the investigator for any other reason: important medical events that may not result in death, be life-threatening, or require hospitalization may be considered serious, based upon appropriate medical judgment.

In addition to the above criteria, AEs meeting either of the below criteria, although not serious per International Conference on Harmonisation (ICH) definition, are reportable in the same timeframe as SAEs to meet certain local requirements.

Therefore, these events are considered serious for collection purposes:

- is a new cancer (that is not a condition of the study);
- is associated with an overdose.

Although all AEs after signing the ICF are recorded in the eCRF, SAE reporting begins after the patient has signed the ICF and has received study treatment. However, if an SAE occurs after signing the ICF, but prior to receiving study treatment, it needs to be reported ONLY if it is considered reasonably possibly related to study procedure.

Study site personnel must notify Lilly or its designee of any SAE within 24 hours of investigator awareness of the event via a Lilly approved method. If alerts are issued via telephone, they are to be immediately followed with official notification on study-specific SAE forms. This 24-hour notification requirement refers to the initial SAE information and all follow-up SAE information.

Pregnancy (during maternal or paternal exposure to study treatment) does not meet the definition of an AE but should be reported. However, to fulfill regulatory requirements any pregnancy should be reported following the SAE process to collect data on the outcome for both mother and fetus.

Investigators are not obligated to actively seek AEs or SAEs in patients once they have discontinued and/or completed the study (the patient summary CRF has been completed). However, if the investigator learns of any SAE, including a death, at any time after a patient has been discharged from the study, and he/she considers the event reasonably possibly related to the study treatment or study participation, the investigator must promptly notify Lilly.

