9.2.2. Suspected Unexpected Serious Adverse Reactions

Suspected unexpected serious adverse reactions (SUSARs) are serious events that are not listed in the IB and that the investigator identifies as related to study treatment or study procedure. United States 21 CFR 312.32 and European Union Clinical Trial Directive 2001/20/EC and the associated detailed guidances or national regulatory requirements in participating countries require the reporting of SUSARs. Lilly has procedures that will be followed for the recording and expedited reporting of SUSARs that are consistent with global regulations and associated detailed guidances.

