9.4.2.3. Venous Thromboembolic Events

In the randomized Phase 3 studies in breast cancer patients who received abemaciclib in combination with endocrine therapy, there was a greater number of patients who experienced venous thromboembolic events (VTEs) in the abemaciclib plus endocrine therapy arm than in the placebo plus endocrine therapy arm. The majority of the events were non-serious and were treated with low-molecular-weight heparin. Generally, these events did not result in discontinuation of the study treatment. At this time, the mechanism underlying the association between abemaciclib and the occurrence of VTEs is not known. For suspected or confirmed VTE (eg. deep vein thrombosis or pulmonary embolism), treatment should occur according to usual clinical practice.

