10.3.2. Safety Analyses

All patients who receive at least 1 dose of any study therapy will be evaluated for safety and toxicity.

The National Cancer Institute (NCI) Common Terminology Criteria for Adverse Events (CTCAE) v 4.0 will serve as the reference document for choosing appropriate terminology for, and grading the severity of, all AEs and other symptoms. For AEs without matching terminology within the NCI -CTCAE v 4.0 criteria, the investigator will be responsible for selecting the appropriate system organ class and assessing severity grade based on the intensity of the event.

Both the CTCAE code and the AE verbatim text will be mapped by Lilly or its designee to corresponding terminology within the Medical Dictionary for Regulatory Activities (MedDRA) Version 18.1 (or higher). Adverse events will be reported using a process which includes both CTCAE v4.0 and MedDRA:

- In CTCAE version 4.0, each CTCAE term is a MedDRA lower level term (LLT), except in the case where the CTCAE term is a MedDRA System Organ Class (SOC) followed by 'Other – specify'.
- The CTCAE v4.0 term reported by the investigator will be mapped to the MedDRA Preferred Term (PT) and SOC of the corresponding MedDRA LLT, unless the reported CTCAE term is 'Other – specify'.
- If the reported CTCAE term is 'Other – specify', the MedDRA LLT, PT, and SOC mapped from the verbatim AE term will be used.
- All listings and summaries will use the PT resulting from this process. The LLT will be used in the treatment-emergent computation.

The following safety analyses will be based on the safety population. Safety analyses will be conducted by treatment arm and will include summaries of the following:

- AEs, including severity and possible relationship to study drug
- SAEs, including possible relationship to study drug
- AEs leading to dose adjustments
- discontinuations from study treatment due to AEs or death
- treatment-emergent abnormal changes in laboratory values
- treatment-emergent abnormal changes in vital signs
- extent of exposure

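### Section 9.2 defines a reasonable possibility of relatedness as an existing causal link, which conflicts with the possibility-level wording used elsewhere in the protocol

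*Protocol*

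**What the plan says.** Section 9.2 sets the judgment as a yes/no question: "The investigator will interpret and document whether or not an AE has a reasonable possibility of being related to study treatment or a study procedure". The sentence that follows supplies the only definition of the key phrase in the protocol. A reasonable possibility, it says, "means that there is a cause and effect relationship between the study treatment and/or study procedure and the AE". The verb is unqualified.

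One paragraph earlier, the same section describes the recording duty in weaker terms: "Investigators should record their assessment of the potential relatedness of each AE to study procedure or study treatment via eCRF".

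Other sections rely on the judgment. Section 7.4.1.1.2.1 speaks of toxicity "defined as an AE possibly related to study treatment per investigator judgment". Section 9.2.1 says of an SAE between consent and first dose that "it needs to be reported ONLY if it is considered reasonably possibly related to study procedure". Section 9.2.2 defines SUSARs as serious events not listed in the Investigator's Brochure "that the investigator identifies as related to study treatment or study procedure". Section 10.3.2 lists among the by-arm safety summaries "AEs, including severity and possible relationship to study drug", and a corresponding summary for SAEs.

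**The concern.** The question and its definition set different thresholds. The question asks whether a causal link is reasonably possible; the definition describes a link that exists. An investigator who thinks a reaction plausible but cannot say that the drug caused it would answer yes to the question as posed and could answer no under the definition.

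The answer has consequences. It feeds the related-AE and related-SAE tables, it determines whether an unlisted serious event counts as a SUSAR, and in a few situations it decides whether the sponsor receives an SAE report at all. In metastatic disease, telling a drug effect from progression is often a matter of plausibility, which is where the two thresholds part. Investigators who follow the definition and investigators who follow the possibly-related wording could classify the same event differently.

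**Working it through.** No arithmetic applies: the point depends on no alpha, power, event count or sample size. The check is to set each place that uses relatedness beside the definition in Section 9.2.

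**Places worded as a possibility, in conflict with the definition**
- Section 9.2, recording in the eCRF: potential relatedness.
- Section 9.2.1, SAE before first dose: reasonably possibly related to procedure.
- Section 9.2.1, SAE learned of after discharge from the study: reasonably possibly related to treatment or participation.
- Section 9.2.1, SAE or death caused by progression: reported only if possibly related.
- Table JPCG.3, follow-up of an ongoing AE or SAE after treatment: possibly related.
- Section 7.4.1.1.2.1, toxicity for dose suspension or cycle delay: possibly related.
- Section 10.3.2, AE and SAE summaries: possible relationship.

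**Places that say plain related, with no qualifier**
- Table JPCG.2, follow-up of AEs and SAEs on treatment.
- Table JPCG.3, reporting after Visit 801.
- Section 9.2, which AEs the investigator must follow.
- Section 9.2.2, SUSARs.

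The terms are therefore mixed, and Table JPCG.3 uses both in one cell. Section 9.2 alone contains three expressions: reasonable possibility, potential relatedness, and an existing causal relationship.

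**What the literal definition would reach**
1. The relatedness classification, and so the related-AE and related-SAE summaries in 10.3.2.
2. SUSAR identification, since 9.2.2 takes the investigator's judgment.
3. The three kinds of SAE report in 9.2.1 that depend on relatedness: before first dose, after discharge, and progression-related.
4. AE reporting after Visit 801, which Table JPCG.3 limits to events related to the drug or the study protocol.

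**What it would not reach**
1. Recording of AEs on treatment. Section 9.2.1 has all AEs after consent entered in the eCRF.
2. Notification of other on-treatment SAEs. The 24-hour rule in 9.2.1 carries no relatedness condition.
3. The TEAE endpoints. The TEAE definition in Appendix 1 does not require a causal relationship.
4. PFS, response, OS and the sample size.

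**The case against.** The best defence is that the sentence says what kind of link is being judged, causal rather than merely temporal, and does not set a standard of proof. It stands between a request for potential relatedness and a question about reasonable possibility, and the investigator is told to weigh disease, concomitant treatment and other pathology. An experienced investigator would probably read it that way. This stands as an account of what was likely meant. It does not remove the defect, because the sentence is written as a definition and its plain words say something else.

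The defence also rightly rules out several stronger readings.

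- A reader might infer that plausible but unproven reactions must be recorded as unrelated. No passage orders this. The protocol nowhere uses proven or established causality as the test, and the eCRF instruction points the other way.
- A reader might infer that every rule using relatedness is set at possibly related. Four places are not, as listed above.
- A reader might take venous thromboembolism as the proof case, because Section 9.4.2.3 says that "the mechanism underlying the association between abemaciclib and the occurrence of VTEs is not known". An unknown mechanism does not prevent a causal judgment, least of all when the same paragraph reports an excess in randomized studies.
- A reader might size the problem from diarrhea. The rates in Section 5.5 (about 77% at 200 mg and 80% at 150 mg) give 0.77 × 75 = 57.75 to 0.80 × 75 = 60 patients per arm. That counts patients with diarrhea, not misclassified events. Diarrhea is among the most common AEs on the drug and would probably be called related under either threshold. The rates also come from another study, and Arm C here receives loperamide prophylaxis.
- A reader might infer a bias between arms. The same definition applies in all three, and nothing in the document shows a differential effect.

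**Conclusion.** The point holds as a contradiction in wording with limited reach. Section 9.2 defines a possibility as an existing causal link, against its own recording instruction and against the possibility-level wording in Sections 7.4.1.1.2.1, 9.2.1 and 10.3.2 and Table JPCG.3. Followed literally, it could lower the related-AE and related-SAE counts, narrow SUSAR identification, and suppress some of the reports that depend on relatedness.

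The size cannot be derived from the document. It depends on two unknowns: the share of events that are plausible but not clearly causal, and the share of investigators who follow the definition rather than the surrounding text. Any percentage put on the loss would only return the assumption behind it.

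The conclusion assumes that at least some sites apply the definition as written. If all read it as describing the type of link, classification is unchanged and only the inconsistency of terms remains. The tolerability comparison through TEAEs and SAEs, and all efficacy results, stand either way.

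**What to change.** In Section 9.2, reword the definition so that a reasonable possibility means that a causal relationship between the treatment or procedure and the AE may exist. Then use one relatedness term with that meaning in Tables JPCG.2 and JPCG.3 and in Sections 9.2, 9.2.1, 9.2.2 and 10.3.2. For the toxicity definition in Section 7.4.1.1.2.1, ask only that its wording be reconciled with 9.2; no dosing rule needs to be set or changed for this.

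The cost is one reworded sentence, the matching edits of terms in an amendment, and the same wording in the eCRF completion guideline. The downside is that somewhat more AEs will be classed as related and a few more reports will be expedited.
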